### 2.1. Research question 1 (impact on maternal nutrition practices)

For impact estimates, outcome measures related to maternal diet will be used from the PW datasets, and outcomes to IFA consumption and early breastfeeding practices will be used from the RDW data.

Table 2: Outcome measures for RQ1

Outcome	Indicator	Data source
Maternal dietary diversity and adequate intake	
Primary outcome:
 
 
- Dietary diversity score (# of food groups)
 
 
Secondary outcomes:
 
 
- % PW consumed at least 5 food groups (minimum dietary diversity)
 
- Mean probability of adequacy of micronutrients
 
- % PW consumed and quantity of each food group
 
- Energy, carbohydrate, protein and fat consumption
 
	PW survey PW 24h dietary recall
IFA consumption	
Primary outcome:
 
 
- # of IFA tablets consumed
 
 
Secondary outcomes:
 
 
- % RDW consumed 180+ IFA tablets
 
- # of IFA tablets received
 
	RDW survey
Early breastfeeding practices	
Secondary outcomes:
 
 
- % infants <6 months breastfed within 1h of birth
 
- % infants <6 months with no pre-lacteals fed
 
- % infants <6 months exclusively breastfed
 
	RDW survey

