beginning as early as possible to prevent maternal anemia, puerperal sepsis, low birth weight, preterm birth, maternal anemia and iron deficiency [14]. Ideally, pregnant women should receive IFA tablets no later than the first trimester, corresponding to 6 months (180 days) of supplementation. Ninety-seven percent of women in Boucle du Mouhoun and Hauts-Bassins reported taking at least one IFA or iron tablet during their most recent pregnancy, with 70.6% and 86.0% of women taking at least 90 tablets, respectively [13].

According to the 2017 PMA2020 nutrition survey, calcium supplementation is not common [13]. WHO currently recommends daily calcium supplementation (1.5-2.0 g oral elemental calcium) in populations with low dietary calcium intake to reduce the risk of pre-eclampsia. However, in Burkina Faso calcium supplementation during pregnancy is not yet recommended until further evidence becomes available.

Women's dietary diversity is poor. The mean dietary diversity score (out of 10 food groups) among recently-pregnant women is 3.9 in both regions, slightly higher than the national average of 3.4 [13]. Health providers are nearly twice as likely to provide women information on the importance of diet quality (such as eating a variety of foods and high iron foods) during pregnancy than the importance of quantity (i.e. eating extra food) during ANC services [13].

ANC services are provided in nearly all health facilities, and ANC services are offered, on average, 5-6 days per week [11]. Weighing, nutrition counseling, and IFA supplementation are routine ANC services. Weight gain monitoring during pregnancy is important as body mass index and gestational weight gain are indicators of maternal nutrition and are associated with pregnancy outcomes. Among women who attended ANC during their most recent pregnancy during the past two years, nearly all of them were weighed at least once. However, among them, only 62% of women reported receiving information about their weight gain. This proportion was 72.7% in Hauts-Bassin, higher than in Boucle du Mouhoun. [13]. Roughly half of all facilities support community health workers to provide nutrition services.

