2.4 Outcomes

The primary outcome indicators of the study are focused on diet quality and IFA supplementation. These include:

- 1) **Maternal dietary diversity among pregnant women**
 - i. Mean number of food groups consumed by pregnant women
- 2) **Use of iron-folic acid (IFA) supplements among RDW**
 - i. Mean number of IFA tablets consumed during pregnancy

The secondary outcomes relate to exposure to and utilization of key maternal nutrition, weight gain monitoring, and early breastfeeding interventions, as well as health worker knowledge and capacities at the points of service delivery. These include:

- 3) Maternal diet quality: proportion of pregnant women who achieve minimum dietary diversity; and micronutrient, protein and energy adequacy among pregnant women compared to the recommended dietary intake
- 4) Proportion of women who received 90+ IFA supplements during pregnancy
- 5) Early initiation of breastfeeding and exclusive breastfeeding practices of children
- 6) Use of ANC services (total number of ANC visits/contacts at facility and community levels and timing of the first ANC visit)
- 7) Exposure to nutrition interventions during ANC, including weight gain monitoring (proportion of women who are weighed and counselled about adequate weight gain, total number of times women are weighed during pregnancy)
- 8) Exposure to nutrition information from community health workers (proportion of women who were visited at home during pregnancy, total number of times visited), community groups, and other sources
- 9) Health worker knowledge on benefits and service provision for IFA supplementation, dietary diversity counselling, weight gain monitoring, and breastfeeding counselling
- 10) Availability of service supports (IFA supplies, records/registers, weight measurement equipment, counseling materials, and training and supervision for health workers)

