6.2 Protocol amendments

All amendments to the protocol will be reported (by IFPRI Co-Investigators) to and agreed upon with Alive & Thrive. Any modifications to the protocol which may impact the safety of participants or the scientific validity including changes of study objectives, study design, participants, sample sizes, and study procedures will be reviewed by the IFPRI IRB and the local IRB.

Version control using protocol version identifiers and dates will be used to track the history of amendments and identify the most recent protocol version.

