### 1.2 Impact evaluation study design

The impact evaluation of A&T's interventions used a cluster-randomized design with repeated cross-sectional surveys at baseline and endline. We applied stratified random allocation to 80 health centers (CSPS, Centre de Santé et de Promotion Social) within four health districts (Boromo, Toma, Dande, and Lena), which were assigned to either the A&T intervention (40 CSPS) or control areas (40 CSPS). The baseline survey was conducted in November-December 2019 and the endline survey was conducted in January-March 2021 in the same 80 CSPS catchment areas, thereby creating panel data at the CSPS level (not at individual level). Program implementation duration was approximately 12 months, with a couple of months of interruption due to the COVID-19 pandemic in March-April 2020.

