### III. Statistical Analysis Plan

#### 3.1 General principles and methods

Data analyses will be performed using STATA version 16.0 (StataCorp LLC). All applicable statistical tests will be two-sided to allow potential findings of unexpected effects. Statistical significance will be presented at levels of  $p<0.05$ ,  $p<0.01$ , and  $p<0.001$ .

A diagram presenting the flow of clusters and individuals through the trial, based on the Consolidation Standard of Reporting Trials (CONSORT) statement: extension to cluster randomized trials (Campbell et al., 2012; Eldridge et al., 2016), is shown as follows.

[figure not shown]

Figure 1. CONSORT flow diagram for repeated cross-sectional surveys

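### The protocol's secondary outcome of receiving 90 or more IFA supplements is missing from the SAP, which lists consuming 180 or more instead without explanation

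*SAP*

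**What the plan says.** Protocol section 2.4 lists the secondary outcomes by number. Outcome 4 is the "Proportion of women who received 90+ IFA supplements during pregnancy". It is binary, concerns receipt, and has its cut-off at 90.

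SAP section 2.1, Table 2, lists two secondary outcomes under IFA consumption among recently delivered women (RDW). One is the percentage for "RDW consumed 180+ IFA tablets", which is binary, concerns intake and has its cut-off at 180. The other is the number "of IFA tablets received", a count with no cut-off.

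Both figures appear in the background of protocol section 2.1. Earlier-survey results are cited for the two regions, "with 70.6% and 86.0% of women taking at least 90 tablets, respectively", and starting IFA no later than the first trimester is described as "corresponding to 6 months (180 days) of supplementation". Neither remark defines an outcome.

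On timing, SAP section 1.2 states that "the endline survey was conducted in January-March 2021", so the text was written after fieldwork. The analyses are still to come: "Data analyses will be performed using STATA version 16.0" (SAP section 3.1).

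**The concern.** A numbered secondary outcome has dropped out between protocol and SAP, and a binary outcome that differs in two respects stands in its place. Receipt reflects supply and service delivery; intake also reflects adherence. Protocol Table 1 treats these as separate strands of the intervention: providing enough supplements at each visit, and counselling on daily use. The intervention could move one without the other.

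The cut-offs also look at different parts of the distribution, so an effect could be visible at 90 and not at 180, or the reverse.

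If the SAP is followed as written, the 90+ proportion goes unreported. Because the substitution is unexplained and sits in a document written after endline fieldwork, a reader could suspect that the outcome was chosen for its result. Nothing in the documents supports that suspicion, but nothing in them answers it either.

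**Working it through.** **Comparison of the outcome lists.** The claim is about which outcomes are listed, so there is no stated figure to reproduce.

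| Place | Measure | Type | Cut-off |
|---|---|---|---|
| Protocol 2.4, primary | tablets consumed | mean | none |
| Protocol 2.4, outcome 4 | supplements received | proportion | 90+ |
| SAP Table 2, primary | tablets consumed | count | none |
| SAP Table 2, secondary | tablets consumed | proportion | 180+ |
| SAP Table 2, secondary | tablets received | count | none |
| SAP Table 6 (dummy table) | tablets consumed | count and proportion | none; 180+ |

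SAP Tables 3, 4 and 7 contain no tablet-count threshold either. No 90+ indicator, received or consumed, appears anywhere in the SAP's lists, and no 180+ outcome appears in the protocol. The primary outcome matches.

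**How far apart the cut-offs lie (illustration only).** The documents give no distribution for tablets received and no SD for tablets consumed. Both cut-offs are therefore applied to tablets consumed, X, under a normal approximation with the baseline mean of 108.64 from protocol section 2.5: P(X ≥ c) = 1 − Φ((c − 108.64)/SD).

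One SD can be backed out of the sample-size statement, treating it as a single two-arm comparison (15 tablets, 960 per arm, ICC 0.206, two-sided 5%, 80% power):

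- Women per cluster: 960/40 = 24.
- Design effect: 1 + 23 × 0.206 = 5.738.
- Effective n per arm: 960/5.738 = 167.3.
- SD = 15 / [(1.960 + 0.842) × √(2/167.3)] ≈ 49.

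| SD | P(X ≥ 90) | P(X ≥ 180) |
|---|---|---|
| 40 (assumed) | 67.9% | 3.7% |
| 49 (implied) | 64.8% | 7.3% |
| 60 (assumed) | 62.2% | 11.7% |

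**Reconciling with the earlier survey.** The 70.6% and 86.0% in protocol section 2.1 are higher than these values at 90. They can be matched in two ways:

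- Hold the mean at 108.64 and shrink the SD. For 70.6%, SD = 18.64/0.542 = 34.4, which gives 1.9% at 180+. For 86.0%, SD = 18.64/1.080 = 17.3, which gives under 0.1%.
- Hold the SD at 40, 49 or 60 and shift the mean. For 70.6%, means of about 112, 117 and 123 give about 4%, 10% and 17% at 180+. For 86.0%, means of about 133, 143 and 155 give about 12%, 22% and 34%.

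Across all these cases, 62–86% of women reach 90 and 0–34% reach 180.

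**The case against.** The textual discrepancy is not in dispute; the arguments against go to its weight and to the remedy.

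- **Limited reach.** One secondary outcome is affected. The primary IFA outcome is the same in both documents, and receipt is kept as a count. Protocol section 6.7 promises public anonymised data, so the proportion might be derived later. This stands as a limit on severity. It does not replace a planned, reported analysis.
- **180 has a natural origin.** The 180-day remark in protocol section 2.1 could explain the new threshold. Neither document makes that link, and it would not explain the move from receipt to intake.
- **A reason may exist elsewhere.** The SAP's opening pages were not available, so the absence of a reason, and of a version date, is established only for the text that was. The missing row in Tables 2 and 6 does not depend on those pages.
- **The SAP lists may not be exhaustive.** They do not say that they are. What is certain is that the SAP does not specify the 90+ outcome; non-reporting is the likely result of following it.
- **The illustration is indirect.** It concerns consumption, not receipt, and treats a bounded count as normal. Backing the SD out of a difference-in-difference (DID) contrast of four independent groups (√(4/167.3) in place of √(2/167.3), with no correlation between survey rounds) gives about 34.6, outside the assumed 40–60. That yields 70.5% at 90+ and 2.0% at 180+, within the overall ranges above. The figures show only that the cut-offs are not interchangeable.
- **Declaring the outcome dropped would also remove the contradiction.** It would, if dated and justified. Restoring it costs almost nothing and loses no information, so it is the better course.

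**Conclusion.** The concern holds. The SAP's outcome list contradicts the protocol's: a pre-specified proportion on receipt at 90+ is absent, and a proportion on intake at 180+ appears in the same place with no explanation in the available text.

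This rests on comparing the lists and needs no distributional assumption. The percentages assume normality and an SD that the documents do not supply. They describe consumption only and make no claim about power.

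The change should be made, but it does not threaten the trial's main conclusion, since the primary IFA outcome and the sample size are untouched. There is no evidence that outcome data influenced the change. No view is taken on which cut-off is clinically preferable.

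**What to change.** 1. In SAP Table 2, under the secondary outcomes for IFA consumption, add the percentage of RDW who received 90+ IFA supplements, with a reference to protocol section 2.4, outcome 4. Derive it from the tablets-received variable already planned, and report the unadjusted and adjusted DID estimates as SAP section 3.3 does for other outcomes.
2. Keep the 180+ consumed row, labelled as added in the SAP. State the date, the reason, and whether endline outcome data had been accessed by then.

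Protocol section 6.2 sets a suitable model for the note: "Version control using protocol version identifiers and dates will be used to track the history of amendments". That commitment covers protocol amendments and does not mention the SAP, so the note would apply the same practice there.

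The cost is one table row, one further outcome run through the planned unadjusted and adjusted models, and one dated note. No new data are needed.

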## 2.2 Research question 2 (coverage and utilization)

For effects on coverage and utilization of interventions during ANC visits, outcome measures will be used from the RDW survey data. In the context of the overall evaluation, outcomes under this research question are considered as secondary outcomes.

Table 3: Outcome measures for RQ2

Outcome	Indicator	Data source
ANC visits and contacts	
 
- # of ANC visits (at health facility)
 
- Total # of ANC contacts
 
- % RDW with at least 4 ANC visits
 
- % RDW with at least 8 ANC contacts
 
- % RDW received ANC visit in first trimester of pregnancy
 
- # of contacts outside of health facility (home visits and GASPAs)
 
	RDW survey
Counseling on dietary diversity and adequate intake	
During ANC visits and other ANC contacts:
 
 
- % RDW received counseling on maternal nutrition
 
- % RDW received counseling on dietary diversity
 
- % RDW received counseling on consuming adequate quantity of food
 
	RDW survey
Counseling on IFA supplementation	
During ANC visits and other ANC contacts:
 
 
- % RDW received counseling on importance of IFA
 
- % RDW received counseling on how/reminders to take IFA
 
- % RDW received counseling on managing IFA side effects
 
	RDW survey
Weight gain monitoring and counseling	
During ANC visits and other ANC contacts:
 
 
- # times weighed
 
- % RDW weighted at least 4+ times/at each ANC visit
 
- % RDW received counseling about weight gain during pregnancy
 
	RDW survey
Counseling on early breastfeeding practices	
During ANC visits and other ANC contacts:
 
 
- % RDW received counseling on breastfeeding practices
 
- % RDW received counseling on early initiation of breastfeeding
 
- % RDW received counseling on not feeding pre-lacteals
 
- % RDW received counseling on exclusive breastfeeding
 
	RDW survey

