4.1.5 Pregnant women questionnaire

Detailed interviews with pregnant women will be conducted in their homes at baseline and endline. Information on household composition, household socioeconomic status, household food security, dietary diversity, obstetric history, use of ANC, social desirability, and maternal nutrition and breastfeeding knowledge will be collected. The modules in questionnaire are presented in **Table 8**.

Table 8: Description of modules in pregnant women questionnaire

Module	Topic	Description	Respondent
1	Identification	Name, ethnicity, religion, phone number	Enumerator
2	Household roster	Information on the composition of the household, including designation of the head of household, a list of all household members, their ages and sex, and their relationship to the pregnant woman, and the highest educational level attained and activity/employment	Pregnant woman
3	Obstetric history	Age at first marriage, last menstrual period, gestational age, number of pregnancies, number of living children, date of last birth	Pregnant woman
4	Use of antenatal care (facility-based)	Frequency and timing of ANC use and exposure to nutrition counseling and messages during facility-based ANC contacts	Pregnant woman
5	Exposure to maternal nutrition interventions in the community	Exposure to maternal nutrition counseling and messages during home visits and community meetings and gatherings	Pregnant woman
6	Consumption of IFA	Current consumption of IFA tablets, receipt/purchase of IFA tablets; observation of IFA tablets/packs/bottles	Pregnant woman
7	Dietary diversity	Dietary diversity of the pregnant woman and household in the past 24 hours	Pregnant woman
8	Maternal health and nutrition knowledge and perceptions	General knowledge on health and nutrition, nutrition during pregnancy, anemia, and IFA supplementation; perceptions about maternal nutrition	Pregnant woman

		and roles of husbands, other family members and community/village	
9	Food security	Prevalence of household hunger using the FANTA household food insecurity access scale (HFAS)	Pregnant woman
10	Dwelling	House construction (materials used for floor, walls, and roof), availability of water and electricity, sources of fuel/energy for cooking, WASH facilities	Pregnant woman
11	Assets	Ownership of durable household goods (in working condition), including tools for agricultural production	Pregnant woman
12	Social desirability	Desire for social approval	Pregnant woman

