### 3.3 Impact estimates

The main analysis of impacts will be performed using intent-to-treat (ITT) specifications, wherein all study participants in the originally assigned program group at baseline are included in the statistical analysis and analyzed according to their program group, regardless of whether they received interventions or not. Women who refused or withdrew consent or those who are ineligible according to study protocol are excluded from ITT analysis.

The main impacts of the interventions will be estimated for: (1) maternal diet during pregnancy, (2) consumption of IFA supplements, and (3) early breastfeeding practices; secondarily, impact will be estimated for exposure to key interventions: (4) maternal nutrition counseling, (5) counseling on IFA supplementation, (6) weight gain monitoring and counseling, (7) breastfeeding counseling. The impact on dietary diversity will be assessed among PW, and impact on all the remaining outcomes will be assessed among RDW.

The difference-in-difference (DID) method will be used to estimate impacts by comparing the changes in outcomes over time (baseline vs. endline) between study arms (intervention vs. control). Point estimates and changes in the outcomes will be reported. For the analysis, the Stata *diff* command will be used, accounting for clustering at the CSPS level with a cluster version of Huber-White robust estimator of standard errors and using degrees of freedom appropriate for the number of CSPS (Hayes & Moulton, 2017). The fixed effects in the two-level regression models will be study arm, survey time, and arm times survey; the latter estimates the difference between arms in changes over surveys. We will conduct ITT analyses based on the original evaluation design, as well as the adjusted ITT analyses using the ITT groups but adjusting for gestational age (for PW only), maternal characteristics, child age and sex (for RDW only), and other variables that may be different between study arms.

Table 6: Dummy table for impact estimates

Indicator	Baseline		Endline		Unadjusted DID	Adjusted DID
	A&T (N=)	Control (N=)	A&T (N=)	Control (N=)		
	Mean (SD)	Mean (SD)	Mean (SD)	Mean (SD)	pp	pp
Dietary diversity score (number of food groups)						
Number of IFA tablets consumed						

	Percent	Percent	Percent	Percent	
Minimum dietary diversity ( $\geq 5$ food groups)					
Consumed 180+ IFA tablets					

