#### 3.4.2. Analysis of program impact pathways

The program impact pathway (PIP) was developed in collaboration with the A&T program team to map out the mechanisms through which the interventions were expected to achieve impact. The purpose of

the PIP analysis is to lay out the theoretical causal links between program activities, outcomes, and impacts. We will examine key indicators along the components of pathways (addressed in part by RQ2 and RQ3), to interpret and support the impact evaluation results. We will compare differences between program groups for indicators along the pathway matched to the relevant outcomes (dietary diversity, IFA consumption, and breastfeeding practices), using mixed-effects regression models, accounting for geographic clustering. Additional path analyses will be considered based on the results of the above analyses.

Table 7: Measures for program impact pathways

Outcome	Key Indicators	Data source
Service providers' capacity-building and service provision:		
Training and supervision (RQ3)	
 
- % NM received maternal nutrition training
 
- % ASBC received maternal nutrition training
 
- % NM/ASBC by training content
 
- % NM/ASBC received supervision
 
- % NM/ASBC by supervision content
 
	N-M survey ASBC survey
Service providers' knowledge (RQ3)	
 
- Knowledge scores for dietary diversity, adequate intake, IFA, and weight gain monitoring
 
- Knowledge scores for breastfeeding
 
	N-M survey ASBC survey
Service provision (RQ3)	
 
- % NM/ASBC provided maternal nutrition interventions
 
- % NM/ASBC by counseling messages provided (on dietary diversity, IFA, weight gain monitoring, and breastfeeding)
 
- % NM/ASBC used job aids for maternal nutrition counseling
 
- % ASBC provided home visits to PW/number of visits in last 30 days
 
- % ASBC conducted GASPA for PW/number of meetings in last 30 days
 
	N-M survey ASBC survey
Beneficiaries' exposure and behavioral determinants:		

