ANC visits and contacts (RQ2)	
 
- # of ANC visits (at health facility)
 
- Total # of ANC contacts
 
- % RDW with at least 4 ANC visits
 
- % RDW with at least 8 ANC contacts
 
- % RDW received ANC visit in first trimester of pregnancy
 
- # of contacts outside of health facility (home visits and GASPA)
 
	PW survey RDW survey
Counseling on dietary diversity and adequate intake (RQ2)	
During ANC visits and other ANC contacts:
 
 
- % RDW received counseling on maternal nutrition
 
- % RDW received counseling on dietary diversity
 
- % RDW received counseling on consuming adequate quantity of food
 
	PW survey RDW survey
Counseling on IFA supplementation (RQ2)	
During ANC visits and other ANC contacts:
 
 
- % RDW received counseling on importance of IFA
 
- % RDW received counseling on how/reminders to take IFA
 
- % RDW received counseling on managing IFA side effects
 
	PW survey RDW survey
Weight gain monitoring and counseling (RQ2)	
During ANC visits and other ANC contacts:
 
 
- # times weighed
 
- % RDW weighted at least 4+ times/ at each ANC visit
 
- % RDW received counseling about weight gain during pregnancy
 
	PW survey RDW survey
Counseling on early breastfeeding practices (RQ2)	
During ANC visits and other ANC contacts:
 
 
- % RDW received counseling on breastfeeding practices
 
- % RDW received counseling on early initiation of breastfeeding
 
- % RDW received counseling on not feeding pre-lacteals
 
	PW survey RDW survey

	
 
- % RDW received counseling on exclusive breastfeeding
 
	
Beneficiaries' knowledge and perceptions	
 
- Knowledge scores for dietary diversity, adequate intake, IFA, and weight gain monitoring
 
- Knowledge scores for breastfeeding
 
- Beliefs, self-efficacy, and social norms score
 
	PW survey RDW survey

Table 8: Dummy table for program impact pathways analysis

Indicator	Baseline		Endline	
	A&T (N=)	Control	A&T	Control
	Mean (SD)			
(see indicators in Table 7)				
	Percent			

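### The impact estimate for first-trimester ANC uses only recently delivered women, whose early pregnancies mostly overlapped the pre-launch period or the COVID interruption; add an estimate in pregnant women

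*SAP*

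**What the plan says.** Early ANC is a programme target: Protocol Table 1 lists reminders on early attendance, promotion of a first-trimester visit and identification of pregnant women for early ANC. Timing of the first visit is part of secondary outcome 6 in Protocol 2.4.

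For research question 2, SAP 2.2 says: "For effects on coverage and utilization of interventions during ANC visits, outcome measures will be used from the RDW survey data". Its Table 3 includes the percentage of "RDW received ANC visit in first trimester of pregnancy", with the RDW survey as the only source. SAP 3.3 repeats the rule for the difference-in-difference (DID) analysis: "The impact on dietary diversity will be assessed among PW, and impact on all the remaining outcomes will be assessed among RDW".

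SAP Table 7 lists the same block of ANC indicators for the pathway analysis and names both the PW and the RDW survey as sources, but the first-trimester indicator is still labelled as a percentage of RDW. Of these indicators SAP 3.4.2 says: "We will compare differences between program groups for indicators along the pathway matched to the relevant outcomes".

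On dates, SAP 1.2 says "The baseline survey was conducted in November-December 2019", puts the endline survey in January-March 2021, and describes about 12 months of implementation "with a couple of months of interruption due to the COVID-19 pandemic in March-April 2020". Protocol 1.3 has the intervention start once baseline is complete. Neither document gives a launch date.

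The PW questionnaire (Protocol 4.1.5, Table 8) records last menstrual period and gestational age, and also "Frequency and timing of ANC use and exposure to nutrition counseling and messages during facility-based ANC contacts".

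**The concern.** RDW are the natural sample for outcomes that need a completed pregnancy, such as total tablets consumed or eight contacts. First-trimester attendance is settled much earlier. A woman interviewed with an infant under 6 months was in her first trimester roughly 6 to 15 months before the interview. For an endline in early 2021, that reaches back to the months before launch and through the March-April 2020 interruption.

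A woman whose early pregnancy fell partly outside active delivery had less chance of being prompted to attend early. Averaged over the RDW sample, this pulls the estimated effect on early ANC toward zero. A weak result could then reflect the programme or simply the calendar, and the specified impact analysis would not separate the two.

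**Working it through.** The documents give no figure for this overlap, so there is none to reproduce. I worked back from their dates.

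**Inputs from the documents.** RDW have a living child under 6 months (Protocol 2.2). Endline is January-February 2021 in Protocol 1.3 and January-March 2021 in SAP 1.2. The interruption is March-April 2020 (SAP 1.2). Samples are 480 PW and 960 RDW per arm.

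**Assumptions.** Launch is 1 January 2020 (varied below). Delivery stops from 1 March to 30 April 2020 and otherwise continues to endline. Gestation is 280 days, child age uniform over 0-182 days, PW gestation uniform over 6-40 weeks, and interviews are spread evenly over the survey period. The window in which a first-trimester visit can be prompted is weeks 4-13, that is, days 28-90 after the last menstrual period (LMP), 63 days.

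**RDW: window wholly in active delivery**
- LMP = interview date - child age - 280 days.
- January plus February 2020 is 31 + 29 = 60 days, shorter than 63, so no window fits between launch and the interruption.
- The window must therefore start on or after 1 May 2020: LMP on or after 1 May - 28 days = 3 April 2020, hence birth on or after 3 April 2020 + 280 days = 8 January 2021.
- At a mid-survey interview on 13 February 2021, the qualifying births are those of 8 January to 13 February, 37 of 183 possible child ages, or 20%. Averaging over all interview dates gives the table.

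| Endline interviews | Wholly active | Mean share active, launch 1 Jan | Mean share active, launch 1 Feb |
|---|---|---|---|
| 1 Jan-28 Feb 2021 | 13% | 59% | 45% |
| 15 Jan-15 Mar 2021 | 21% | 63% | 52% |
| 1 Jan-31 Mar 2021 | 21% | 62% | 52% |

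Counting conventions for days move the second column by about a point, so I quote 13-22%: 0.13 × 960 = 125 to 0.22 × 960 = 211 women per arm.

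For the middle row with a January launch, the window days divide into 4% before launch, 33% in March-April 2020, 25% in January-February 2020 and 37% after April. Active time is 25% + 37%, about 63% before rounding.

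**RDW: other launch dates.** Launch on 15 December 2019 gives a mean active share of 63-65%. Launch on 1 March 2020 gives 30-38%, with 45-54% of women having no active day in the window.

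**PW at or past 13 weeks**
- With gestation uniform over 42-280 days, about 79% are at or past day 91: 0.79 × 480 ≈ 380 per arm.
- The earliest LMP for an interview on 15 January 2021 is 15 January - 280 days = 10 April 2020, so the window opens on 8 May 2020, after the interruption.
- Over the three survey periods, 99.8-100% have the window wholly after 30 April 2020.
- The programme's end date is not given either. If delivery had stopped on 31 December 2020, the mean active share in these women would still be 89-95%.

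**Precision.** For an endline comparison of proportions (80% power, two-sided 5%, control 33-50%, assumed intra-cluster correlation 0.11), the detectable difference is about 12 points with 960 RDW per arm (design effect 1 + 23 × 0.11 = 3.53, effective n 272). It is about 14 points with 350 PW per arm, slightly fewer than the 380 above (1 + 7.75 × 0.11 = 1.85, effective n 189). A DID comparison needs larger differences in both samples. Because clustering dominates, losing more than half the women costs about 2 points.

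**The case against.** **Overlap is not absence.** A reader might infer that RDW first trimesters nearly all fell before launch or in the interruption. They did not. With a January launch more than half of the window was active, almost no woman had no active day, and over a third of window days came after April 2020. The 13-22% figure is a strict measure, since a single visit suffices and a woman can be prompted in any active week. This stands: the effect is diluted, not removed. SAP 1.2 also does not say that all facility and community promotion stopped for two full months, so the true active share may be higher.

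**A false finding of no effect cannot be predicted.** That would need an effect size and a confirmed launch date, and the documents give neither. Only the direction of the bias follows.

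**PW are not ignored.** It would be wrong to say that early ANC is assessed only in RDW. Table 7 names the PW survey for this block in the between-group pathway comparison. What remains is that PW are absent from the DID specification, and that Table 7 has no PW definition and disagrees with Table 3 on source.

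**RDW were chosen deliberately.** Intention-to-treat in RDW estimates the programme as delivered, interruption included, and the SAP describes the endline as already conducted. Making a PW subset the main estimate because its exposure is more favourable would be open to challenge. That stands, and is why the PW estimate should be added rather than substituted.

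**Conclusion.** The point holds in a limited form. The impact estimate for first-trimester ANC is specified in RDW only. Most endline RDW pregnancies overlapped non-delivery time in weeks 4-13: about 13-22% had the window wholly active, and on average about 60% of it was active (about 45-52% with a 1 February launch). The estimate is therefore diluted toward zero. PW at or past 13 weeks had the window almost entirely after April 2020, and the data needed are already in their questionnaire.

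The size rests on an undocumented launch date, a full two-month stop, 280-day gestation and uniform age distributions. The direction does not depend on the launch date, because March-April 2020 alone takes about a third of the RDW window. The outcome is secondary, so this is a low-cost improvement and not a threat to the primary conclusions.

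**What to change.** 1. In SAP Table 3 and 3.3, keep the RDW estimate of first-trimester ANC and add a prespecified estimate by the same DID model in PW at or beyond 13 completed weeks at each survey. The restriction matters because an earlier-gestation woman without a visit may still attend in time.
2. In Table 7, define the matching PW indicator, with the same gestational restriction, so that label and source agree, and reconcile the source with Table 3.
3. State beside the RDW result that it covers pregnancies that partly preceded launch or overlapped the interruption, and give the actual launch and interruption dates so the overlap can be calculated.
4. State that the PW estimate supplements the RDW one, and whether it was specified before endline data were examined.

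The cost is some SAP wording and one further secondary model on data already collected. The added estimate uses about 380 rather than 960 women per arm, so its interval will be wider.
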